7.1.1. AEs of Special Interest

Adverse events of special interest related to low dose aspirin use include:

- Major bleeding events (as defined by the International Society on Thrombosis and Hemostasis as fatal bleeding, symptomatic bleeding in a critical area or organ, or bleeding causing a decrease in hemoglobin of 2g/dL or more or leading to a transfusion of 2 or more units of blood)
- Minor bleeding events (all other clinically significant bleeding events not addressed by the above criteria)
- Medication intolerance (defined as intolerable medication side effects or adverse medication reaction)

7.1.2. Reporting of AEs

The study team, including PI, will be alerted in the event of an AE. AEs will be reported as required by the Institutional Review Board as described above.

11.2 Serious Adverse Events

An AE is considered "serious" if in the opinion of the investigator it is one of the following outcomes:

- Fatal
- Life-threatening

- Constitutes a congenital anomaly or birth defect
- A medically significant condition (defined as an event that compromises subject safety or may require medical or surgical intervention to prevent one of the three outcomes above).
- Requires inpatient hospitalization or prolongation of existing hospitalization
- Results in persistent or significant incapacity or substantial disruption to conduct normal life functions.

7.2.1. Reporting of SAEs

The study team, including PI, will be alerted in the event of an serious AE. Serious AEs will be reported as required by the Institutional Review Board as described above.

11.3 Emergency Unblinding of Investigational Treatment

Not applicable

11.4 Other Reportable Information

Pregnancy tests are conducted as standard of care prior to initiation of chemotherapy for women of reproductive age. The research team will be notified in the event of pregnancy and the patient will be withdrawn from the study.

11.5 Special Warnings and Precautions

As above, pregnancy tests are conducted as standard of care prior to initiation of chemotherapy for women of reproductive age. The research team will be notified in the event of pregnancy and the patient will be withdrawn from the study.

11.6 Stopping Rules

Any patient with medication intolerance or clinically significant bleeding will be withdrawn from the study to minimize harm. In the event of chemotherapy-induced thrombocytopenia with platelet count less than 50,000, participants will be asked to hold aspirin for 1 week until platelet counts normalize.

11.7 Safety Oversight Committee (SOC)

Since this is a pilot phase IV study, the safety oversight committee is not applicable.

11.8 External Data and Safety Monitoring Board (DSMB)

No member of the research team, including the PI, has a potential conflict of interest with the conduct of this protocol.

12 QUALITY CONTROL AND QUALITY ASSURANCE

12.1 Monitoring

This clinical research study will be monitored both internally by the PI, and institutionally by the Duke Cancer Institute (DCI). In terms of internal review the PI will continuously monitor and tabulate adverse events. Appropriate reporting to the Duke University Medical Center IRB will be made. If an unexpected frequency of Grade III or IV events occur, depending on their nature, action appropriate to the nature and frequency of these adverse events will be taken. This may require a protocol amendment, dose de-escalation, or potentially closure of the study. The PI of this study will also continuously monitor the conduct, data, and safety of this study to ensure that:

- Interim analyses occur as scheduled;
- Stopping rules for toxicity and/or response are met;
- Risk/benefit ratio is not altered to the detriment of the subjects;
- Appropriate internal monitoring of AEs and outcomes is done;
- Over-accrual does not occur;
- Under-accrual is addressed with appropriate amendments or actions;
- Data are being appropriately collected in a reasonably timely manner.

DCI Protocol Review and Monitoring systems (PRMS) review of this protocol begins with an initial review by the Cancer Protocol Committee (CPC). CPC new protocol review focuses on scientific relevance, study design, adequacy of biostatistical input, protocol prioritization, feasibility of completing the study within a reasonable time frame and risk assessment of the trial. The PI will abide by CPC assessment of the level of risk, which will determine the intensity of subsequent DCI monitoring. CPC also conducts annual scientific progress reviews on protocols that are open to enrollment and focus on protocol prioritization, accrual and scientific progress. These reviews are conducted at the time of IRB annual renewals and documentation of all CPC reviews will be maintained in eIRB/iRIS systems.

A determination for the degree of monitoring conducted by the DCI monitoring team is made at the time of initial CPC approval to commensurate with the type and level of intervention, phase, endpoints, degree of risk, size and complexity of the protocol. A formal, independent monitoring will be conducted by the DCI monitoring team according to the risk level and monitoring plan assigned by the CPC until the study is closed to enrollment or subjects are no longer receiving study drug or other interventions that are more than minimal risk. Additional monitoring may be prompted by findings from monitoring visits, unexpected frequency of serious and/or unexpected toxicities, or other concerns. Monitoring visits may also be initiated upon request by DUHS and DCI Leadership, CPC, SOC, a sponsor, an investigator, or the IRB.

The DCI monitoring team reviews the adequacy of informed consent, enrollment of eligible patients, implementation of protocol-specified procedures and treatment, adequacy of data collection, and appropriateness of adverse event monitoring and reporting. The DCI monitoring team presents final monitoring reports to the DCI Safety Oversight Committee (SOC) highlighting safety concerns and unresolved issues. The SOC, at a convened meeting, assigns an overall rating of satisfactory, marginal, or unsatisfactory to reflect the overall quality of data, regulatory, consent, eligibility, study conduct and AE reporting. Corrective action plans (CAPs) are developed, implemented, and evaluated as indicated. The SOC will notify the sponsor-investigator and DUHS IRB when significant safety concerns are identified.

The SOC in concert with DCI monitoring team conducts data and safety monitoring for DUHS sponsor-investigator phase I and II, therapeutic interventional oncology studies that do not have an independent DSMB. These reviews occur at a minimum annually and more frequently for the high risk studies. The SOC safety reviews include review of safety data, enrollment status, stopping rules if applicable, accrual, toxicities,

reference literature, and interim analyses as provided by the sponsor-investigator. The SOC, at a convened meeting, assigns a rating of satisfactory when adequate accrual with lack of excessive toxicity is present.

12.2 Data Management and Processing

8.3.1. Case Report Forms (CRFs)

The electronic CRF in REDCap will be the primary data collection document for the study. The CRFs will be updated in a timely manner following acquisition of new source data. Only approved study staff as approved in Key Personnel are permitted to make entries, changes, or corrections in the CRF.

An audit trail will be maintained automatically by the electronic REDCap CRF management system. Designated personnel will complete user training, as required or appropriate per regulations.

8.3.2. Data Management Procedures and Data Verification

Designated personnel using the electronic CRF will have access based on their specific roles in the protocol. These are outlined in the REDCap system and all requests must be approved by the owners of the database (PI, coordinators). Only individuals specified as Key Personnel will be included.

Completeness of entered data will be checked automatically by the eCRF system, and users will be alerted to the presence of data inconsistencies. Additionally, the data manager and research team coordinators, [name] and [name], will cross-reference the data to verify accuracy. Missing or implausible data will be highlighted for the PI requiring appropriate responses (i.e. confirmation of data, correction of data, completion or confirmation that data is not available, etc.).

The database will be reviewed and discussed prior to database closure, and will be closed only after resolution of all remaining queries. An audit trail will be kept of all subsequent changes to the data.

8.3.3. Study Closure

Following completion of the studies, the PI will be responsible for ensuring the following activities:

- Data clarification and/or resolution
- Accounting, reconciliation, and destruction/return of used and unused study drugs
- Review of site study records for completeness

13 STATISTICAL METHODS AND DATA ANALYSIS

All statistical analysis will be performed under the direction of the statistician designated in key personnel, [name]. Any data analysis carried out independently by the investigator must be approved by the statistician before publication or presentation.

13.1 Analysis Sets

The analysis set will include data from the study cohort for the duration of the defined study period. Considerations for data analysis are outlined below.

13.2 Patient Demographics and Other Baseline Characteristics

Baseline characteristics analyzed will include age, body mass index, CA-125 at diagnosis, Khorana score, ECOG performance score, and number of cycles of neoadjuvant chemotherapy.

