3.2 Background and Significance

VTE is a known potential complication of malignancy and is particularly common among women with epithelial ovarian cancer (EOC).^[1,2] In addition to having active cancer, women with EOC are predisposed to other well-established risk factors for VTE, including impaired mobility, increasing age, and advanced disease.^[3] The risk of VTE is even greater among patients with clear cell histology, thrombocytosis, high grade tumors, and co-morbid cardiovascular risk factors (e.g., obesity, hypertension, diabetes).^[4-7] In a recent study at our institution, we found that women with advanced ovarian cancer receiving NACT are at high risk for VTE with an incidence of nearly 8%.^[8]

Importantly, the occurrence of VTE among patients with EOC is associated with increased morbidity, decreased survival, and increased healthcare costs.^[9-11] Timely interval debulking surgery and the ability to achieve of optimal surgical debulking also remain critical components of care for advanced EOC. In the aforementioned study, we observed that the average time from start of NACT to interval debulking surgery was longer for patients who experienced a VTE during NACT as compared to those who had not; these patients were also less likely to have their disease optimally debulked at the time of interval surgery. The high incidence of VTE during NACT reported in our study as well as the associated morbidity contributes to a growing body of evidence suggesting that thromboprophylaxis during NACT is warranted.

According to the current guidelines from the American Society of Clinical Oncology, thromboprophylaxis with either apixaban, rivaroxaban, or low molecular weight heparin (LMWH) is recommended for high risk ambulatory cancer patients (defined as a Khorana score greater than or equal to 2) receiving systemic chemotherapy. Patients with a primary gynecologic malignancy receive one point in the Khorana score at baseline, and the majority of ovarian cancer patients would meet criteria for an additional point. High risk Khorana scores defined as 3 or greater have a 6.7-7.1% risk of VTE which is similar to the incidence defined in the previously described study of patients receiving NACT for advanced EOC. These patients are therefore considered high risk for adverse thromboembolic events when initiating systemic chemotherapy.

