DOAC instead. Any existing patients with a Khorana score of more than 1 who have already completed their aspirin regimen and are considered "on follow up" will remain on study.

Once enrolled in the study, subjects will receive a 30-day supply of low dose aspirin from a study team member and will be instructed to start taking one 81 mg tablet daily starting the first day of their first neoadjuvant chemotherapy cycle. Subjects may also be consented after the first day of their first cycle so long as they are taking the aspirin by the end of the day of their second cycle. Patients who are already on low dose aspirin for another indication will still be eligible for the study but will be instructed to take the study drug such that adherence can be monitored. These patients will continue their prior regimen following completion of NACT. Participants will be instructed to complete medication adherence diaries and AE symptom questionnaires. At each subsequent clinic visit for consideration of an additional NACT cycle, a member of the research team will review medication adherence diaries and AE symptom questionnaires and administer the Voils DOSE-Nonadherence measure survey. If symptoms are concerning for a potential AE, the research team personnel will inquire further and discuss with the PI. Please see subsequent sections related to AE monitoring and reporting. No additional components of history and physical exam will be completed outside standard of care performed by the patient's provider prior to initiation of an additional cycle of NACT. Different patients may undergo different numbers of NACT cycles, and thus the 30-day supply of aspirin will be refilled by a member of the research team when the decision is made to proceed with an additional cycle.

Participants who experience clinically significant adverse drug events such as bleeding or medication intolerance will be withdrawn from the study. Subjects with significant chemotherapy-induced thrombocytopenia (platelet count less than 50,000) will be instructed to stop taking daily aspirin for 1 week until platelet counts normalize. If a subject withdraws from the study voluntarily, there will be no further follow up. If a participant is censored due to development of a VTE or clinically significant AE, the research team will continue to collect clinical data until the end of the predetermined follow up period.

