8.7.2. Statistical Hypothesis, Model, and Method of Analysis

The goal for initiating accrual into this study will be September 1st, 2020. Patients will continue to be enrolled through December 30th, 2021. Subjects will be followed through the primary NACT treatment course until interval debulking surgery, with an estimated duration of 6-9 months following enrollment depending on the number of NACT cycles the individual undergoes. The primary efficacy outcome of this study is rate of VTE among the study cohort during NACT. The primary safety outcome is the incidence of clinically significant adverse drug events. Data from medication adherence diaries and AE symptom questionnaires will be reviewed and entered into the REDCap database. An intention-to-treat analysis will be performed. Subjects withdrawn due to medication intolerance or adverse drug events will be censored, and the research team will continue to collect clinical data for the predetermined follow up period.

We will calculate the incidence of VTE during the study period defined above (enrollment to interval debulking surgery or 1 week after completion of the primary neoadjuvant chemotherapy course if debulking surgery is deferred) and estimate a 95% exact binomial confidence interval. Since this is a pilot study, the incidence of venous thromboembolism in the study population will be compared to a historical control from a previous research study

of the incidence of venous thromboembolism among women receiving neoadjuvant chemotherapy for advanced ovarian cancer in which the majority of patients were from Duke. A drop greater than 20% (from approximately 8% to 6.4%) in the rate of venous thromboembolism would be considered clinically meaningful. If the true VTE rate is 6.4%, the width of the 95% exact binomial confidence interval will be 0.098. We will also monitor for adverse safety events related to low dose aspirin use, including major or minor bleeding events, gastrointestinal complications, and medication intolerance (side effects or adverse reaction). Further detail regarding AE monitoring and reporting is outlined in a previous section.

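### The crude comparison with a historical 8% VTE rate has no check on case mix: Khorana score differs by design, and the baseline list omits four risk factors the protocol names and counts NACT cycles as baseline

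*Combined protocol and SAP*

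**What the plan says.** Section 13.4.2 (printed as 8.7.2) says the trial's VTE incidence "will be compared to a historical control from a previous research study", most of whose patients came from the lead institution. Sections 3.6 and 13.6 say the same. The historical rate is about 8%, and a fall of more than 20%, to 6.4%, is called clinically meaningful. The only inferential tool named is a 95% exact binomial interval for the trial's own rate.

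The covariates are in Section 13.2: "Baseline characteristics analyzed will include age, body mass index, CA-125 at diagnosis, Khorana score, ECOG performance score, and number of cycles of neoadjuvant chemotherapy".

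Section 3.2 names the factors that raise VTE risk. One sentence gives "other well-established risk factors for VTE, including impaired mobility, increasing age, and advanced disease". The next gives "clear cell histology, thrombocytosis, high grade tumors, and co-morbid cardiovascular risk factors (e.g., obesity, hypertension, diabetes".

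Since the April 2021 amendment, eligibility requires a Khorana score of 1 (Sections 3.3, 7.1 and 9.1). Earlier patients were enrolled whatever their score, and some with higher scores may remain on study.

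On cycles, Section 3.3 says "Different patients may undergo different numbers of NACT cycles", with aspirin resupplied each time another cycle is decided on. The VTE window in Section 13.4.2 is "enrollment to interval debulking surgery or 1 week after completion of the primary neoadjuvant chemotherapy course if debulking surgery is deferred".

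**The concern.** With one arm and an external comparator, a difference between 8% and the observed rate can come from aspirin, from chance, or from the two cohorts having had different untreated risk. The exact interval addresses chance in the trial's own rate. Nothing in the plan addresses the third source. No column of historical characteristics is planned, and no subgroup or standardised historical rate.

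The amendment makes this more than a general worry. Restricting entry to Khorana 1 excludes new patients with high platelets or a BMI of 35 or more, while Section 3.2 lists thrombocytosis and obesity among the factors that raise VTE risk. The comparator stayed at 8%. If that figure comes from a cohort of mixed scores, the restricted trial would be expected to show a lower rate without any drug effect. A reader could then credit aspirin with a drop that eligibility produced. An imbalance the other way in an unrecorded factor could hide a real effect.

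**Working it through.** **1. The plan's own figure.** Planned enrolment is 60 + 60 = 120 (Sections 7.1 and 10). At 6.4%, 0.064 × 120 = 7.68 events, rounded to 8. The exact (Clopper-Pearson) 95% interval for 8/120 is 2.92% to 12.71%, width 0.0979. This reproduces the stated 0.098, so the plan works with 120. The target is (0.080 − 0.064) × 120 = 1.92 events.

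**2. Section 3.2 risk factors against the Section 13.2 list.**

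| Factor in 3.2 | Covered in 13.2? |
|---|---|
| Age | Yes |
| Obesity | Yes, as BMI |
| Thrombocytosis | Through the Khorana platelet item |
| Impaired mobility | Roughly, through ECOG |
| Advanced disease | Not listed; largely fixed by eligibility |
| Clear cell histology | No |
| High grade | No |
| Hypertension | No |
| Diabetes | No |

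The Khorana items in Section 3.3 are cancer site, BMI, haemoglobin or red cell growth factor use, leukocytes and platelets. Matching on Khorana would therefore leave the last four rows unseen.

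**3. Number of cycles.** The count builds up one decision at a time inside the VTE window, so it is not a baseline value. Section 3.2 reports that "the average time from start of NACT to interval debulking surgery was longer for patients who experienced a VTE during NACT". A VTE may therefore affect the course of NACT, and possibly the count.

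**4. Khorana mix (illustration; f, g and RR are assumed).** Let f be the historical share with Khorana 2 or more, RR their relative risk against Khorana 1, and aspirin have no effect. The expected rate in a Khorana 1 cohort is 0.08 / [1 + f(RR − 1)].

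- f = 0.5, RR = 1.25: 0.08 / 1.125 = 7.11%
- f = 0.5, RR = 1.5: 0.08 / 1.25 = 6.40%
- f = 0.5, RR = 2: 0.08 / 1.5 = 5.33%
- f = 0.8, RR = 2: 0.08 / 1.8 = 4.44%

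The whole 20% drop needs f(RR − 1) = 0.25, that is RR = 1.5 at f = 0.5 or RR = 1.31 at f = 0.8. Patients enrolled before the amendment dilute this. If a share g of the trial also has Khorana 2 or more, multiply by 1 + g(RR − 1). With g = 0.1, f = 0.5 and RR = 1.5, the rate is 0.064 × 1.05 = 6.72%, a fall of 1.28 points or 80% of the target.

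**5. One unlisted factor (illustration; all inputs assumed).** With prevalence ph in the historical cohort and pt in the trial, the expected trial rate is 0.08 × [1 + pt(RR − 1)] / [1 + ph(RR − 1)].

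| RR | 50% v 40% | Share of 1.6 points | 50% v 30% | Share of 1.6 points |
|---|---|---|---|---|
| 1.5 | 7.68% | 20% | 7.36% | 40% |
| 2 | 7.47% | 33% | 6.93% | 67% |
| 3 | 7.20% | 50% | 6.40% | 100% |

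Reversed, with 40% historically and 50% in the trial at RR 2, the rate rises to 0.08 × 1.5 / 1.4 = 8.57%, which would mask 0.57 points of benefit.

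**6. Against chance.** An observed rate at or below 6.4% means at most 7 events in 120. Its probability is 24.7% if the true rate is 8%, 49.5% if case mix alone has moved it to 6.40%, and 69.0% if to 5.33%.

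**The case against.** Several points on the other side stand.

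- The list is not blind to VTE risk. Age, BMI, Khorana score and ECOG are there, and a list introduced by a word such as include need not be exhaustive. A reader might infer that the baseline table can say nothing about risk. That is too strong. What is missing is four named factors and the historical column. No other section lists further covariates.
- A reader might infer that cycle count is known only once the outcome period is over, or that the plan means to adjust for it. Neither is supported. The last cycle falls inside the window, and Section 13.2 gives the variable no adjustment role. That a VTE changes the number of cycles is also an inference, since Section 3.2 reports a longer time to surgery and not more cycles. The point about cycles is one of labelling.
- A reader might infer that case mix is shown to be the main threat. It is not. At 8/120 the interval of 2.9% to 12.7% contains 8%, and chance alone gives 6.4% or lower about a quarter of the time.
- This is a pilot, and a longer descriptive list does not remove bias. Both are true. But efficacy is a primary objective with a stated threshold for a meaningful drop. That is why the repair has to reach the comparison as well as the list.

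**Conclusion.** The point holds. The plan has no means of separating an aspirin effect from a case-mix difference in a comparison whose target is 1.6 percentage points, or 1.92 events in 120. The one imbalance visible in the documents is Khorana score, which is already on the list but is not used in the comparison. The omission of histology, grade, hypertension and diabetes, and the baseline label on cycle count, are secondary and easily corrected.

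The documents establish that confounding is possible, not how large it is. They give neither the Khorana mix nor the covariates of the historical cohort, and no relative risks. Under the assumed ranges, one unlisted factor gives 20% to 100% of the target drop. A Khorana difference could give all of it or more if higher scores were common in the historical cohort. If that cohort was in fact similar in Khorana score, the largest part of the concern falls away. The plan as written would not show this.

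**What to change.** 1. In Section 13.2, add histology (clear cell or other), grade, hypertension and diabetes.
2. Move number of NACT cycles to Section 13.3 and report it as treatment exposure.
3. In Section 13.4.2, tabulate the same variables for the historical cohort beside the trial.
4. In Section 13.4.2, add one supportive comparison: the trial rate against the historical rate in Khorana 1 patients, or against the historical rate standardised to the trial's Khorana mix. The standardised rate is w1 × r1 + w2 × r2, where w1 and w2 are the trial's shares with Khorana 1 and with 2 or more, and r1 and r2 are the historical rates in those groups. Report it with an interval that reflects the historical counts. State that a crude drop from 8% will not be attributed to aspirin without this comparison.

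The cost is abstraction of routine chart fields, one extra table and one extra estimate. It depends on access to the earlier study's patient-level data, which is plausible because that study is described as the institution's own, but is not confirmed. Precision is limited by the number of historical events in each Khorana group, which the documents do not give, so the figure can only be supportive. If the data cannot be reached, the report should say so and present the comparison with 8% as descriptive.
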